5.6 Study duration

The Karisma-1 pilot trial (Eudra CT2014-005-005-20) preceded the Karisma-2 trial. The major focus of the pilot trial was to estimate time to mammographic density change. In all, 32 healthy women completed the 6 month trial and were exposed to 10 or 20 mg/day of oral tamoxifen.

The results of the Karisma-1 trial showed a mammographic density decrease after the full study period of 6 months, of about 50% for one quarter of the participants. For another quarter of the participants

a \approx 20% mammographic density decrease was seen. The remaining 50% of the participants did not experience any change in mammographic density.

Table 1 displays the change in mammographic density among the 32 patients seen after 3, 6 and 9 month of follow up. The biggest decrease is seen the first 3 months and the decrease continues even after the treatment was stopped at 6 months.

Table 1. Mean percent dense area and density change from baseline in percent in the Karisma-1 pilot study (n=32), in relation to months in study.

	0 month	3 months	6 months	9 months
Mean % dense area	17.6	15.8	15.3	14.6
Mean % change from baseline	-	-1.8	-2.3	-3.0

The results of the Karisma-1 pilot trial show that 3 months of oral tamoxifen exposure is enough to significantly influence mammographic density. Since it could be that the uptake of topical endoxifen, in contrast to oral tamoxifen, is slower, the treatment period in Karma CREME-1 trial has been set to 6 months, with mammograms and density measurements performed at 3 and 6 months.

5.7 Conclusion

The ability of oral tamoxifen to reduce breast cancer risk is well-accepted and proven. The tamoxifen metabolite endoxifen has the highest affinity for the estrogen-receptor of the tamoxifen metabolites. The ability of topical endoxifen to penetrate the skin of the breast was demonstrated in the phase 1 study of topical endoxifen without safety or tolerability signals. Topical endoxifen, at doses 10 and 20 mg/day will therefore be tested using mammographic density change as the outcome. The arguments for topical endoxifen are:

1. Endoxifen has the highest affinity of all the tamoxifen metabolites to the estrogen-receptor.
2. The liver is not required to metabolize endoxifen and interference with the coagulation pathway system and liver function is less likely to occur.
3. From a theoretical point of view, endoxifen applied to the skin covering the breast could be enriched in the breast tissue because the high affinity to the estrogen receptor and the vascularisation of the breast epithelium.
4. Directed delivery to the breast with limited systemic exposure may result in better tolerability and compliance.

6 BENEFIT-HARM ASSESSMENT

6.1 Background

In a broader sense, ethical considerations in clinical trials should focus on answering the question – does knowledge generated through the trial outweigh the possible harms inflicted on the participants? The most important task is to take the safety of study participants into consideration. Breast cancer incidence has increased rapidly over the last generations and currently one women per minute is diagnosed with breast cancer in Europe. It could therefore be argued that efforts taken to reduce the number of breast cancers are much needed. Tamoxifen has been used for adjuvant therapy for breast cancer for several decades and the side effects of tamoxifen are well-known. Side effects range from menopausal symptoms and mood swings to increased risks of endometrial cancer and thromboembolism. Tamoxifen has also been found to reduce the number of newly diagnosed cancers in perfectly healthy women but is not used to any larger extent due to the risk of bothersome as well as potentially very serious side-effects. Little is known about the side effects of endoxifen. Therefore, a conservative approach must be to assume that the toxicity of endoxifen is identical to that of

tamoxifen and that there is a dose dependency is used. The following sections discuss the potential risks associated with exposing healthy volunteers to topical endoxifen and the associated mitigation strategies. Possible benefits of participating in the trial are also described, as well as benefit-harm assessment of frequent mammograms.

6.2 Safety

The most serious side effects of tamoxifen are thromboembolic events, endometrial cancer, sarcoma of the uterus and liver damage such as cirrhosis and steatosis. Markers of the coagulation system, liver function and levels of sex hormone binding globulin (SHBG) were therefore tested in the phase I topical endoxifen trial. Comparing levels before trial initiation and at 28 days of exposure to the study drug revealed no influence on these parameters, not even in the highest dose (10 mg) category. For more detailed information on the phase 1 results, please see Investigator Brochure.

During pregnancy, tamoxifen and its metabolites interact with rapidly growing and developing embryonic or foetal tissues. Tamoxifen exposure during pregnancy could lead to congenital malformations, spontaneous abortions and even foetal deaths.

6.2.1 Risk mitigation strategy -Safety

The phase 1 data does not indicate a systemic influence on the systems but since it cannot entirely be ruled out that there is an effect on the coagulation system, liver function or SHBG, markers of their function will be measured at 3 and 6 months in this phase 2 study.

Patients with a previous cardiovascular event will be excluded from the study. Blood pressure will be measured before entering the study and women with a blood pressure $>140/90$ mm Hg will not be included in the trial. Possible signs of vaginal bleeding will be addressed immediately. Since only postmenopausal women will be included, pregnancy related safety issues are not a concern.

6.3 Tolerability

Theoretically, topical endoxifen could give two kind of side effects, local and systemic. The local problems emanate from the application of the solution to the skin of the breast. The systemic effects from circulating plasma endoxifen and are measured as experienced side effects through using self-reported answers to a Functional Assessment of Cancer Therapy – Endocrine Subscale (FACT-ES) questionnaire. The comprehensive questionnaire covers all the well-known side effects seen for tamoxifen, such as physical, social, emotional and functional wellbeing. Additional concerns are hot flushes, night and cold sweats, vaginal discharge, etc.

6.3.1 Local side effects

Local irritation, redness and itching, were the most commonly reported symptoms in the topical endoxifen phase 1 trial, which mostly spontaneously resolved during treatment but in one case lead to the discontinuation of the study drug. Mild itching, pain and redness was seen in all dose categories, even placebo. Moderate problems were seen in 4 individuals in the highest dose group and in one participant in the lowest dose group. No severe skin problems were reported.

A self-administered assessment was performed daily by the women as to local tolerance. **Table 2** shows the results of the assessments. As can be seen, most problems were scored as mild, some few moderate and none as severe. It turned out that the majority of the reports (41%) of burning, itching, and particularly irritation was reported by one study subject.

Table 2. Results of Local Tolerance Self-assessment

Parameter	None n (%)	Mild n (%)	Moderate n (%)	Severe n (%)	Total n
Redness	662 (98.5)	10 (1.5)	0 (0.0)	0 (0.0)	672
Burning	669 (99.6)	3 (0.4)	0 (0.0)	0 (0.0)	672
Pain	661 (98.4)	10 (1.5)	1 (0.1)	0 (0.0)	672
Itching	651 (96.9)	16 (2.4)	5 (0.7)	0 (0.0)	672
Irritation	651 (96.9)	20 (3.0)	1 (0.1)	0 (0.0)	672

6.3.1.1 Risk mitigation strategy - Local side effects

It is important that participants are encouraged to only apply the product to intact and not to broken skin. Should local symptoms emerge, consultation with the study staff should be made to determine if continued participation is warranted. The participants will also be asked to:

- Not expose the treated skin to sunlight (natural or artificial), as the photosensitivity properties of the product have not been established
- Avoid skin to skin transfer if possible, at least 30 minutes after application
- Avoid exercise, swimming or bathing for at least 30 minutes after application

6.3.2 Systemic side effects

In the topical endoxifen phase 1 study systemic side effects were measured using the FACT-ES. The most common side-effects of tamoxifen and thereby possibly endoxifen are hot flushes, amenorrhea, altered menses, vaginal discharge, depression, mood swings, nausea, oedema, fatigue and breast pain/tenderness. None of these symptoms were seen among the 25 participants of the phase 1 trial.

What was seen was abnormal dreams, hypersomnia, vomiting and headache, however, not in a dose-dependent manner. The group that had most participants experiencing side effects was the placebo group and the most common symptom in this group was headache. As can be seen in **Table 3** there were reports of mild to moderate symptoms from a variety of organs but, with the exception of skin problems, there does not seem to be a dose dependency. The table gives the number of individuals reporting problems.

Table 3. Number of individuals reporting treatment emergent adverse events by severity and dose in the topical endoxifen phase 1 trial

System Organ Class, Preferred Term	Severity	Active Cohort				Total Placebo (n = 7)	All Subjects (n = 25)
		2 mg (n = 6)	6 mg (n = 6)	10 mg (n = 6)	Total Active (n = 19)		
Infections and infestations							
	Moderate					1 (14%)	1 (14%)
	Mild	1 (17%)	1 (17%)	3 (50%)	5 (28%)	-	5 (20%)
Psychiatric disorders							
	Mild	2 (33%)	-	-	2 (11%)	-	2 (8%)
Nervous system disorders							
	Moderate	-	1 (17%)	-	1 (6%)	2 (29%)	3 (12%)
	Mild	1 (17%)	-	1 (17%)	2 (11%)	1 (14%)	3 (12%)
Vascular disorders							
	Mild	-	-	-	-	1 (14%)	1 (4%)
Gastrointestinal disorders							
	Moderate	-	1 (17%)	-	1 (6%)	1 (14%)	2 (8%)
	Mild	-	2 (33%)	-	2 (11%)	1 (14%)	3 (12%)
Skin and subcutaneous tissue disorders							
	Mild	-	1 (17%)	2 (33%)	3 (17%)	-	3 (12%)
Reproductive system and breast disorders							
	Moderate	1 (17%)	-	-	1 (6%)	-	1 (4%)
	Mild	-	-	-	-	1 (14%)	1 (4%)
General disorders and administration site conditions							
	Mild	-	-	-	-	1 (14%)	1 (4%)
Investigations							
	Mild	-	-	1 (17%)	1 (6%)	-	1 (4%)
Injury, Poisoning and procedural complications							
	Moderate	-	1 (17%)	-	1 (6%)	-	1 (4%)
	Mild	1 (17%)	1 (17%)	-	2 (11%)	-	2 (8%)

6.3.2.1 Risk mitigation strategy - Systemic side effects

Participants will be informed to immediately contact the Karma Study Centre if they suspect side effects. As within the ongoing dose determination study, Karisma-2 where the aim is to test the effect of low dose tamoxifen, participants have the options of reporting side effects via telephone, mail, internet or the so called Karmapp. Participants get help at the centre in downloading the app at inclusion. Participants are encouraged to report side effects month 1, 3 and 6. They are also encouraged to spontaneously report any problems that could be related to the therapy.

In the Karisma-2 trial, study personal take turns carrying a study mobile phone and participants can reach the Karma Trial Centre during office hours. Exactly the same strategy for reporting side effects will be used in the topical endoxifen phase 2 trial as in the Karisma-2 trial. Participants reporting severe side effects are immediately contacted and discontinuation discussed. So far, 16% of the participants of the Karisma-2 trial have left the study because of side effects.

6.4 Benefit-harm assessment of frequent mammograms

Eligible study participants will only be women that have negative screening mammograms before entering the study, i.e., no abnormalities have been identified. The participants will have extra mammograms taken at 3 and 6 months after study entry. In order to reduce radiation exposure, the mammograms consist of 2 images instead of 4, which are standard at a screening examination. The examinations are performed on a low-dose screening modality and the total effective radiation dose

is less than 0.2 mSv. The mean value of a conventional x-ray examination is 1 mSv. The Radiation Protection Board of Södersjukhuset has approved the Karma CREME-1 study.

The images will be used for density measurement but radiologist will also screen them for abnormalities as in clinical practice. It could be that cancers are diagnosed at these extra visits, which should be seen as something that benefits the study participants.

If a suspected alteration is seen at baseline mammogram, the women will be excluded from the study and receive the normal diagnostic routine work-up for a suspected breast cancer, that is, additional ultrasound examination and a possible fine needle biopsy.

7 SAFETY, TOLERABILITY, EFFICACY AND LABORATORY ASSESSMENTS

7.1 Safety Assessment

- Monitoring and recording Adverse Events (AE) and Serious Adverse Events (SAE). Participant that reports of adverse events will be followed and appropriate medical action taken, (e.g., examination, telephonic contact, etc.) as warranted. Participants can contact Karma Study Centre through phone, mail, visit or using the application Karmapp. Reported Adverse Events defined as AE of interest, for example, severe intensity grade or signs of severe events (see section 10.4 AE of interest) will alert Investigator in the eCRF system for immediate action. This approach was successfully used in the Karisma-1 and 2 trials.
- A Data and Safety Monitoring Board (DSMB) will monitor the safety of the study according to the guidelines described in the DSMB charter. Monitoring will also be executed by an external monitor according to a monitoring plan.
- Blood tests for liver function and coagulation function will be obtained at baseline, 3 and 6 months (see section below, laboratory assessment, for specific testinformation).
- Participants will be provided a wallet sized Participant card containing essential information about the study and contact information to Karma Study Centre (see appendix).
- Participants will be trained and encouraged to report any symptoms or changes they experience.

7.2 Tolerability Assessments

Tolerability will be assessed as a function of two doses of endoxifen dose or placebo. In Karma CREME-1, questionnaires will be used to evaluate general symptoms (Memorial Symptom Assessment Scale), specific symptoms of anti-hormonal treatment (FACT-ES), compliance of medicine intake (Morisky scale). In addition to the revised FACT-ES questionnaire, specific skin-related questions will also be employed to assess local tolerability. Qualitative data will be collected through interviews with some of the participants to get their experiences particularly regarding the IMP in order to design next study for optimal feasibility.

7.3 Efficacy Assessments

Mammographic density will be measured at baseline and after 3 and 6 months. In the Karma CREME-1 study both Volpara and Stratus will be used to analyse the mammographic changes as described in chapter 5 Study Rationale; section 5.5 Mammographic density.

7.4 Laboratory Assessments

Blood tests for safety

Blood tests such as liver function tests (ALT, AST, ASP, Bilirubin), Sex Hormone Binding Globulin (SHBG) and coagulation parameters (INR, aPTT), will be analysed. The analyses will be performed within the routine care at Karolinska University Laboratory. These blood tests will be performed at baseline and at 3 and 6 months following study entry. Abnormal laboratory findings and liver and coagulation parameters changing after baseline will call for attention in the eCRF and alert Investigator for judgment and possible action.

Endoxifen in plasma

It is expected that the topical administration will yield substantially reduced blood levels of endoxifen compared to oral tamoxifen dosing (see section 5.3.2 Plasma endoxifen levels after exposure to tamoxifen). In the phase 1 study of topical endoxifen, low levels of endoxifen were observed in some participants in a dose-dependent manner. The metabolic analyses for Karma CREME-1 will be performed at Clinical Pharmacology, Karolinska University Hospital, Huddinge, with a validated method also used in the Karisma-2 trial.

8 STUDY OBJECTIVES AND ENDPOINTS

8.1 Primary objective: Breast Density Reduction

- Primary objective is to determine the effect size of the breast density change between topical placebo and two doses of topical endoxifen. The effect size will permit sample size calculations for statistical significance in a future phase III trial.

8.1.1 Primary endpoint

- Primary endpoint is to determine change, on an individual level, in mammographic breast density, measured at 3 and 6 months after study entry (=baseline screening-mammography).

8.2 Secondary objective: Tolerability and Safety

- Secondary objective is to assess tolerability and safety of topical endoxifen

8.2.1 Secondary endpoints

- Determine dose dependent differences in compliance, side effects and local tolerability measured through questionnaires

- Determine dose dependent differences in laboratory assessments such as liver function tests (ALAT, ASAT, ALP, Bilirubin), coagulation function (INR, aPTT), sex hormone binding globulin (SHBG)

8.3 Tertiary objective

- The tertiary objective is to determine if plasma levels of endoxifen influence primary and secondary endpoints

8.3.1 Tertiary endpoint

- Tertiary endpoint is to determine if plasma level concentrations of endoxifen are related to primary and secondary endpoints

9 STATISTICAL METHODS AND CONSIDERATIONS

Karma CREME-1 is an exploratory pilot study conducted to aid the planning of a larger phase 2 trial. As such, the pilot study is not powered to show statistical significant reductions in breast density in the treatment arms compared to the control arm. Rather, the pilot study will give qualitative results, which will aid in making decisions about dosing, study length, and sample size for the phase II trial.

The pilot study's inclusion criteria will be the same as in the planned full study, but compliance is expected to be higher since the population is small and there will be a large number of contact points with each study participant. Furthermore, in the pilot study only Karma Cohort participants will be invited. The participants have shown that they are more willing to be recruited in the ongoing oral tamoxifen Karisma-2 trial than the ordinary screening attendant. Data from this pilot study will be used to adequately power a future, larger study.

9.1 Statistical methods and determination of sample size

All analyses will be performed after the study is completed and the database is released. All statistics, including tables, figures and listings, will be performed using SAS[®], Version 9.3, and R, Version 3.x. The statistical analysis are described in detail in the Statistical Analysis Plan (SAP) including a Data Display Plan (DDP), which will be in a final draft version prior to study start and finalized and approved before database lock.

9.1.1 Demographics and baseline data

All data will be presented using descriptive statistics. Continuous variables will be summarized using number of women, mean, standard deviation (for symmetric distributions), interquartile range (for skewed distributions), median, minimum and maximum. Categorical variables will be summarized using the number and percentage of women.

9.1.2 Analysis of the primary endpoint (effectiveness)

The analysis of the primary endpoint qualitatively and quantitatively summarize difference in density change between baseline and at 3 and 6 months follow-up between the three arms. More specifically, the difference in density between baseline and at 3 and 6 months follow-up, respectively, for women in the placebo arm (ΔD_p) and in the two endoxifen arms (ΔD_{e1} and ΔD_{e2}), will be computed. Subsequently, the difference between ΔD_p and ΔD_{e1} as well as ΔD_p and ΔD_{e2} (at both 3 and 6 months) will be assessed.

The primary analysis will be performed on an intention to treat (ITT) basis, and a per protocol (PP) analysis will be performed as a secondary analysis. Women who stop using topical endoxifen will be encouraged to remain in the study and come in for an exit mammography. The density measured in these mammograms will be used in the analyses of the ITT population. Our experience from the Karisma-2 study is that virtually all women accept an exit mammography if choosing to withdraw from the study. However, women who drop out of the study and do not come in for additional

mammography appointments will be assumed to not have any density reduction for the ITT analysis. Sensitivity analyses where density for women who drop out is imputed based on age and density at baseline will also be performed.

Since this is a pilot study, which is not powered for showing statistical significance when testing for differences in mammographic density reduction between the treatment arms and the control arm, a simple criterion based on the difference in the mean of the density reduction across the two treatment arms and the density reduction in the control arm will be used instead. The concept mt is defined as the mean of the reduction in mammographic density across all women in the two treatment arms ($n=60$) and the mc to be the mean on the reduction in mammographic density in the control arm ($n=30$). The result of the trial as mt minus mc will be summarized.

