9.1.3 Trial operating characteristics

Simulations to assess the operating characteristics of the pilot study were performed. The simulations aimed at using the best data currently available to estimate the likely outcomes in the pilot study.

As a basis for the simulations, a dataset of 4,288 women aged 40-74 sampled from the Karma Cohort was used. Each woman had Stratus measured density from two mammograms taken at two different points in time (approximately two years in between the two time points as this is the screening interval in the Swedish national screening program). Summary statistics of the density at the two timepoints:

Time point 1: 25.5% (mean), 18.9% (median), IQR 8.3-35.2, 0.1 (min), 99.2 (max)

Time point 2: 23.3% (mean), 18.7% (median), IQR 8.3-34.4, 0.1 (min), 99.8 (max)

Women with BI-RADS categories B, C, and D will be invited to the Karma CREME-1 study. All women with a BI-RADS A density, which corresponds to women with a STRATUS density measures of 2% or lower ($n=240$), were removed from the dataset. The remaining women were used for simulations.

The following assumptions were used for all simulations:

- Age: 40-74
- BI-RADS: B, C, and D
- The density for women in the control arm is only affected by the natural reduction in density that typically comes with increased age. For simulations under the null, this applied also to the treatment arms
- 65% of the women in the treatment arm are good compliers and are assumed to get the whole density reduction that topical application of endoxifen can induce.
- 25% of the women in the treatment arm are poor compliers and are assumed to get half of the density reduction that topical application of endoxifen can induce.
- 10% of the women in each arm drop out of the study. It was assumed that the probability of dropout is proportional to the density reduction a given woman gets from the treatment (this is consistent with previous data that shows that it primarily is women who get a density reduction of tamoxifen who also experience side effects).
- The density reduction that topical application of endoxifen induces is proportional to each woman's density at baseline.
- Comparison between treatment and control arm will be done using a Wilcoxon test in the full phase II trial using a two-sided alpha=0.05 to declare statistical significance.

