Table 5. The table shows the probabilities of the pilot trial showing a *false positive* result based on different criteria for declaring a positive result from the pilot study. Simulations performed under the null hypothesis of no or only a very small reduction in density induced by topical application of endoxifen

Criterion	Density Reduction		
	10%	12%	14%
mt-mc > 0%	50%	56%	57%
mt-mc > 1%	24%	33%	35%
mt-mc > 2%	8%	16%	17%
mt-mc > 3%	2%	5%	5%

Based on these simulations of the operating characteristics of the trial, the criterion $mt-mc > 0\%$ as a criterion for a positive result from the pilot trial and for moving forward with a larger trial with adequate power for showing a statistically significant density reduction from topical endoxifen will be used.

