10.7.7 Method of assigning participants to treatment groups

- A sequential list of participant identifiers (Rand.id) will be generated by the Investigator, and provided to the sponsor.
- Renaclinical LTD London will populate the sequential list of Rand.id and link dose of IMP (0 mg, 5 mg/sachet or 10 mg/sachet) to Rand.id in a randomized manner. A Randomization list is subsequently created.
- Renaclinical will provide the Randomization list directly to the pharmacy (Apoteket AB, Sjukhusapoteket Linköping) in a secured fashion, to be opened in case of a safety emergency.

- Renaclinical will also provide the Randomization list directly to PPP for blinded labelling and packaging.
- The IMP will be imported and received by Renaclinical. Once released by the QP, it will be sent to Apoteket Kliniska prövningar, Solna.
- IMP will be delivered to study site (Karma Study Centre) already randomized, packed and marked in a sequential order. The IMP will be provided to each participant in numerical order.
- The Investigator link the Rand.id to participant in the eCRF and Drug accountability log

Researchers do not have access to the Randomization list. In case of an emergency, the entire list will not be released, rather the treatment assigned for a specifically identified participant.

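### The effect sizes and mt-mc are raw differences in mean density change; adding baseline density as a covariate would give a modest, nearly free gain in precision.

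*Combined protocol and SAP*

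**What the plan says.** Section 9.1.2 obtains "the difference in density between baseline and at 3 and 6 months follow-up, respectively, for women in the placebo arm" and for each of the two endoxifen arms, and then compares placebo with each dose at 3 and at 6 months. The go/no-go statistic is "a simple criterion based on the difference in the mean of the density reduction across the two treatment arms" and that in the control arm: mt (n=60) minus mc (n=30). No covariate is named. Baseline density is used again only to impute for dropouts in a sensitivity analysis.

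Section 10.7.7 says the randomisation vendor will "link dose of IMP (0 mg, 5 mg/sachet or 10 mg/sachet) to Rand.id in a randomized manner"; it describes no stratification by density. Section 9.1.3 gives the paired data behind the simulations, about two years apart: "Time point 1: 25.5% (mean), 18.9% (median), IQR 8.3-35.2" and "Time point 2: 23.3% (mean), 18.7% (median), IQR 8.3-34.4". It also assumes: "The density reduction that topical application of endoxifen induces is proportional to each" woman's baseline value. Section 8.1 states what the estimate is for: "The effect size will permit sample size calculations for statistical significance in a future phase III trial".

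Section 9.1 refers to a separate, detailed SAP. It is not among the documents supplied and may already adjust for baseline.

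**The concern.** Subtracting baseline removes its influence completely only if change is uncorrelated with baseline. The plan expects otherwise in the active arms, where the effect is taken as proportional to baseline, and its printed figures suggest the same for untreated women. With 30 women per arm and a baseline interquartile range of 8.3-35.2, chance differences of several points in mean baseline density are ordinary. Part of the error in the effect size then comes from a variable already in the database. The effect size is the pilot's stated product, so this avoidable error passes into the sizing of the next trial. It matters more for each dose against placebo than for pooled mt-mc.

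**Working it through.** **1. Reproduce the plan's own figures.** The mean effect multiplier is 0.65 + 0.25 × 0.5 = 0.775 (section 9.1.3: 65% full effect, 25% half, 10% dropout with none). At the 12% best guess the expected mt-mc is 0.12 × 0.775 × 25.5 = 2.37 points. From the first column of Table 5 (24% above 1, 8% above 2), the standard error (SE) of mt-mc is 1/z(0.76) = 1.42 and 2/z(0.92) = 1.42. A normal approximation on this basis gives false negatives for mt-mc > 0 of 8.5%, 5.1% and 2.9% at 10%, 12% and 14%, against 10%, 7% and 3% in Table 4. The match is within 2 percentage points. Table 5's headings repeat 10/12/14%, but its caption reads "Simulations performed under the null hypothesis of no or only a very small reduction in density induced by topical application of endoxifen", so its columns are taken as the 0/1/2% scenarios.

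**2. SD of individual change.** Probit fits to each of the six columns of Tables 4 and 5 give an SE of 1.45-1.68. Dividing by √(1/60 + 1/30) = 0.2236 gives an SD of change of 6.5-7.5; the single-column calculation above gives 1.42/0.2236 = 6.35. The range used is 6.4-7.5.

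**3. Correlation of change with baseline.** For paired measurements,

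r = (SD2² − SD1² − SDchange²) / (2 × SD1 × SDchange).

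The documents give no SDs. SD1 is assumed to be 19-23 (IQR/1.349 = 26.9/1.349 = 19.9, but the distribution is skewed). SD2/SD1 is taken either as 1 or as the ratio of IQR widths, 26.1/26.9 = 0.970.

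- Example, SD1 = 21 and SDchange = 6.4: equal spread gives −6.4/42 = −0.15; IQR shrinkage gives (415.2 − 441 − 41.0)/268.8 = −0.25.
- Whole range, absolute value: 0.14-0.20 with equal spread, 0.24-0.27 with shrinkage.

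**4. Shift from a one-SD chance imbalance.** Restricting to density above 2%, as the plan does, a baseline built from the printed quartiles, maximum and mean has mean about 27.0 and SD about 22.2. The SD of the baseline imbalance is 22.2 × 0.2236 = 5.0 points for 60 v 30, and 22.2 × √(2/30) = 5.7 for 30 v 30. The expected shift is

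[r × SDchange/SD1 + 0.12 × 0.775 × f] × imbalance SD,

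where f is the active arm's share of the imbalance variance (1/3 pooled, 1/2 single dose). Pooled at r = 0.25: (0.25 × 6.4/22.2 + 0.093/3) × 4.96 = (0.072 + 0.031) × 4.96 = 0.51.

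**5. Raw contrast against ANCOVA.** Results from 20,000 simulated trials per setting, 12% proportional effect, SD of change 6.4, with noise constant, square-root or proportional in density:

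| Correlation | Pooled shift | Pooled variance ratio | Single-dose shift | Single-dose variance ratio |
|---|---|---|---|---|
| 0 | 0.16 | 0.98-1.01 | 0.26-0.30 | 0.96-1.00 |
| 0.15 | 0.36 | 0.95-0.97 | 0.48-0.52 | 0.89-0.94 |
| 0.25 | 0.51 | 0.88-0.91 | 0.65-0.68 | 0.83-0.87 |

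Shifts are in density points, against an expected difference of 2.3-2.5. The ratio is ANCOVA over raw. With an SD of change of 7.5 and square-root noise, the pooled shifts are 0.40 and 0.57 and the ratios 0.96 and 0.91 at correlations 0.15 and 0.25. The adjusted estimate had bias below 0.07 points, and 95% intervals with HC3 standard errors covered 95-96%.

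At correlation 0 the pooled contrast gains nothing even though the drug effect is proportional. A common slope weights the active arms by two thirds (0.093 × 2/3 = 0.062), while the best slope for this contrast is 0.031. It overshoots by as much as no adjustment undershoots.

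**The case against.** The strongest reply is that no error is shown. The contrast is unbiased, most baseline variation is already subtracted, and the pilot is deliberately simple and unpowered. In one check at correlation 0.25 the SE of mt-mc fell from 1.50 to 1.43, so a 95% half-width of about 2.9 points became 2.8; the next trial would be sized almost identically. This stands, and it limits the weight of the point.

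The correlation is also inferred, not stated. It rests on an SD taken from a skewed IQR, on rounded probabilities from 1,000 simulations, and on two-year change in women aged 40-74, whereas the trial measures 3 and 6 months in postmenopausal women with image alignment meant to reduce technical noise. This stands too: the pooled gain depends on carry-over.

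The printed falls (0.0 at the lower quartile, 0.2 at the median, 0.8 at the upper quartile, 2.2 in the mean) look like corroboration, but they fit together poorly. The top quarter would have to fall about 8 points on average while the maximum rises from 99.2 to 99.8. They are at most side support; the correlation formula does not use the means.

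Finally, the next trial is planned with a Wilcoxon comparison, for which the raw change and its SD are the direct inputs. That is a reason to keep reporting them, not a reason to leave out the adjusted estimate.

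**Conclusion.** The concern holds as a modest matter of precision, not of bias. As written, section 9.1.2 leaves the per-dose effect sizes and mt-mc unadjusted for baseline density. If the correlation of change with baseline is 0.15-0.25, adjustment lowers the variance by 3-12% for pooled mt-mc and 6-17% for a single dose against placebo, or 2-9% of the SE. False negatives for mt-mc > 0 fall by at most 1.3 percentage points, so the go/no-go decision hardly changes.

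The result assumes that change is analysed in percentage points, that SD1 is 19-23 and the SD of change 6.4-7.5, and that the two-year correlation carries over to 6 months. If that correlation is zero, there is essentially no gain. Confidence is medium, because the correlation is derived and the separate SAP was not seen. The change is worth making because it costs almost nothing and applies to the quantity the pilot exists to estimate.

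**What to change.** - Define the effect size at 3 and at 6 months, for each dose against placebo and for pooled mt-mc, as the arm difference from an ANCOVA of follow-up density on arm and baseline density, on the absolute scale.
- Give 95% confidence intervals with a robust (HC3) SE, because a proportional effect makes the slopes differ by arm.
- Keep the raw mean changes as description. Report the SD of raw change, the residual SD and the correlation of change with baseline, so the next trial can be sized for an adjusted or a Wilcoxon analysis.
- Check the correlation beforehand in the existing dataset of 4,288 women, and rerun Tables 4 and 5 for the adjusted mt-mc.
- If the separate SAP already adjusts, align section 9.1.2 with it.

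The cost is protocol and SAP wording and a rerun of existing simulations, with no new data or visits. If change turns out to be unrelated to baseline, pooled mt-mc loses about 1% of precision.
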